8.3 Other Analyses

Subject global assessment of satisfaction evaluated at the last post-procedure follow-up visit (Day 22 – 14 days post-procedure) will be summarized by product group and tabulated for each rating descriptively using N and percentage of subjects. The ratings of “Very Satisfied” and “Satisfied” will also be combined and summarized descriptively (N, percent of subjects, 95% confidence intervals) by product group. The difference between product groups in the proportion of “Very Satisfied” and “Satisfied” subjects will also be presented with a 95% confidence interval for the difference and evaluated for a treatment difference via Chi-square test.

9 Safety Analysis

Adverse events will be tabulated by product group and listed for inspection.

As per Section 7.1 of the protocol, the following does not meet the definition of an adverse event:

- “Any clinically significant abnormal laboratory findings (if applicable) or other abnormal safety assessments which are associated with the underlying disease, unless judged by the investigator to be more severe than expected for the subject’s condition.”
- Therefore, the Dermatologist (erythema, edema, dryness, and desquamation) and Subject-self assessment (pain, stinging/burning, itching, tightness, redness, and dryness) grades will only be considered adverse events (AE) if they are scored as “Severe”, **or** if the investigator judges them to be more severe than expected in context of the Glycolic Acid treatment procedure.

Treatment emergent AEs are defined as events that start on or after the first product application in the test phase.

AEs will be tabulated according to the current version of the MedDRA. Frequencies and percentages will be presented by product group and overall, for each system organ class, and for each preferred term. Summaries of treatment-emergent AEs (TEAEs), treatment-related TEAEs, TEAEs by severity and treatment-related TEAEs by severity.

Adverse events will be listed for the safety population and separately for the non-randomised subjects. Any serious AEs will also be listed.

10 Interim Analysis

Not Applicable

11 Topline Summary

The following tables will be produced for the topline summary:

Table No.	Description
9.1	Subject Disposition by Treatment Group – All Screened Subjects
9.3.1	Summary of Evaluator Global Assessment Score – Safety Population
9.3.4	Summary of TEWL – Changes from Baseline – ITT Population
9.3.5	Summary of Corneometry – Changes from Baseline – ITT Population
9.4.1	Treatment-Emergent Adverse Events – Safety Population
Listing No.	Description
2.1	Adverse Events – Safety Population

12 Changes to Planned Analysis

There are no changes to the protocol-planned statistical analyses however the analysis populations definitions were updated from the protocol (See Section 5.1 above). This is to update inclusion of one post baseline efficacy assessment for ITT population definition and clarification of what assessments will be analysed as per each population.

13 References

None

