3.4. Study Design and Dose Justification

This study is a randomized, evaluator-blind, single-center and two-arm clinical study designed to evaluate the local tolerance and cosmetic efficacy of a topical skin care formulation in healthy female subjects with moderate to advanced photo-damaged facial skin who have undergone a 70% Glycolic Acid facial peel procedure. Glycolic acid is selected due to its widespread use and favourable tolerance profile. [Sharad]

The test product (Physiogel Calming Relief SPF 20 Cream) is designed for subjects with dry, irritated skin and there is favourable local tolerance clinical data to support its use for application to sensitive, post-procedure skin. The test product will be applied twice daily, as consistent with the marketed instructions for use.

A 7 day washout phase is included to standardize subjects' skin care regimens. Subjects will be provided with a commercially available facial cleanser (Simple Kind

Document Name	Protocol 2017-01-08F 20 Day Cream.doc		
Type	Version	Document Identifier	Effective Date
eldo_controlled	0.0: Current Effective/Current	090032d580e2d8a6	07-Jun-2017 01:32:30
Reason For Issue	Auto Issue		

	2. Sunscreen		
--	--------------	--	--

*Lunchtime application must be at least 3 hours after previous sunscreen application

Subjects will not apply any sunscreen on the day of the facial peel procedure (Day 8), since they will remain at site until the evening (after 5 pm). On the morning of each visit, prior to arriving at the site, subjects will be instructed to cleanse their face and not to apply any test product or sunscreen until after all measurements and assessments have been completed. Before leaving the site, subjects will undergo supervised test product and/or sunscreen application. After leaving the site, subjects should apply the sunscreen a second time, but no sooner than 3 hours after the previous application.

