*Lunchtime application must be at least 3 hours after previous sunscreen application

Subjects will not apply any sunscreen on the day of the facial peel procedure (Day 8), since they will remain at site until the evening (after 5 pm). On the morning of each visit, prior to arriving to the test site, subjects will be instructed to cleanse their face and not to apply any test product or sunscreen until after all measurements and assessments have been completed. Before leaving the site, subjects will undergo test product and/or sunscreen application under supervision. After leaving the site, subjects should apply the sunscreen a second time, but no sooner than 3 hours after the previous application.

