6.3.22. Supervised Test Product Application Post-Procedure

Subjects randomized to test product (Group I) will be instructed to apply the test product as per the labelled usage instructions immediately after the post-procedure, pre-treatment (baseline) assessments are complete. The Investigator or designee will oversee this initial product application. Group II will not apply any test product. Product application will be recorded on the eCRF and subject diary and must happen at least 30 minutes prior to any further instrumental measurements. The Investigator or designee involved in this step must not be involved in any assessments in order to protect the blind.

 GlaxoSmithKline	Document Name	Protocol 2017-01-08F 20 Day Cream.doc		
	Type	Version	Document Identifier	Effective Date
	eldo_controlled	0.0; CURRENT/Effective/Current/Reviewed	090032d580e2d8a6	07-Jun-2017 01:32:30
	Reason For Issue	Auto Issue		

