6.3.23. Instrumental Measurements Post-Procedure, Post-Treatment

Measurements to be taken and recorded as per 6.3.11, 180±15 and 360±15 minutes after completion of the facial peel procedure.

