9.2. General Considerations

9.2.1. Definition of Analysis Populations

All randomized subjects will be included in the intent-to-treat (ITT) population. All subjects with at least one application of product in the test phase (i.e. test product for subjects in Group I or sunscreen for subjects in Group II) will be included in the Safety population.

Subjects will be considered eligible for a Per Protocol (PP) population if they were randomized, received at least one application of test product, had at least one post-procedure, post-treatment assessment available and were compliant with both test and washout products post-procedure. Other considerations for eligibility for the PP population including but not limited to use of concomitant medications will be detailed in the Statistical Analysis Plan prior to database unblinding.

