5.1 Analysis Populations

- All randomized subjects with at least one application of product in the test phase (i.e. test product for subjects randomized to receive test product (i.e. in Group 1) or sunscreen for subjects randomized not to receive test product (i.e. in Group 2)) will be included in the Safety population. Evaluator global assessment of tolerance, evaluator individual and subject individual assessments of tolerance and AE reporting will be based on the Safety population.
- All subjects in the safety population with at least one post-baseline efficacy (TEWL or corneometry) assessment will be included in the ITT population. All efficacy analyses will be based on the ITT population
- All subjects will be considered eligible for a Per Protocol (PP) population if they were randomized, received at least one application of product, had at least one post-procedure, post-treatment assessment available and no protocol violations deemed to affect both the primary tolerance endpoint (Evaluator global assessment) and the efficacy assessments (TEWL, corneometry).

Subjects with a protocol violation that is deemed to affect some, but not all, of the above 3 assessments will be part of the PP population, but their data will be excluded from the assessment at which the protocol violation occurred.

Violations that may lead to the exclusion of data for PP analysis include, but are not limited to, the following:

- Violation of inclusion or exclusion criteria at screening or baseline that may affect any of the above 3 assessments.
- Non-compliance with assigned treatment regimen.
- Use of prohibited treatment or medication before or during the study, which it is felt will affect any of the above 3 assessments.

Violations will be documented in the Population Definitions document. The content of this document will be agreed upon between the Biostatistician and Clinical Research Scientist or designee post database lock but prior to breaking of the study blind.

A PP analysis will be performed for the Evaluator global assessment, TEWL and corneometry if there is more than 10% difference in the number of subjects

evaluable in either of the treatment groups for the ITT and PP populations.

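### SAP 9 gives treatment-emergent AEs no common start; on the natural reading the window opens on Day 8 in Group 1 but only on Day 9 in Group 2

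*SAP*

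**What the plan says.** **Window.** SAP section 9: "Treatment emergent AEs are defined as events that start on or after the first product application in the test phase". Neither a product nor a clock time is named.

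**Gloss.** Nearly the same phrase appears in the Safety population definition. Protocol 9.2.1 explains it as "test product for subjects in Group I or sunscreen for subjects in Group II", and SAP 5.1 agrees: "sunscreen for subjects randomized not to receive test product (i.e. in Group 2)) will be included in the Safety population".

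**Group 1 on Day 8.** Protocol 6.3.22 has test product applied "immediately after the post-procedure, pre-treatment (baseline) assessments are complete", and adds that this "must happen at least 30 minutes prior to any further instrumental measurements". Those further measurements are due "180±15 and 360±15 minutes after completion of the facial peel procedure" (Protocol 6.3.23).

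**Group 2 on Days 8 and 9.** Note 12 of the Schedule of Events has Group 2 put nothing on the face at that step. The regimen text in Protocol section 5 excludes sunscreen for everyone on the peel day: "Subjects will not apply any sunscreen on the day of the facial peel procedure (Day 8"). On later visit mornings subjects are "not to apply any test product or sunscreen until after all measurements and assessments have been completed" (Protocol 3.4). The first scheduled post-peel sunscreen is therefore the supervised application at Visit 4, Day 9 (Protocol 6.4.12), after the 24±4-hour assessments.

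**Outputs.** AE Tables 9.4.1 to 9.4.4 contain treatment-emergent events only, and 9.4.1 is in the topline set (SAP 11). Listing 2.1 covers AEs of the Safety population without that restriction. Its study-day footnote counts from the day of first treatment.

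**The concern.** A treatment-emergent table shows how often events occur in each arm over a comparable period. Here the no-product arm supplies the background of reactions caused by the peel alone. If its window opens a day late, that background is missing for the first day after the peel, when peel reactions are expected, while the same reactions count in the test-product arm. With identical true risk in both arms, the definition alone would give Group 1 more subjects with a treatment-emergent AE. The study-day count in Listing 2.1 has the same weakness, because first treatment is not defined for an arm that receives no test product.

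**Working it through.** The plan states no figure for the window, so there is none to reproduce. The opening times follow from the schedule.

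**Inputs, as time after peel completion**
- Group 1 first application: immediately after the baseline at 60±15 min, so about 0.75 to 1.25 h.
- Group 2 first sunscreen: after the assessments at 24±4 h, so about 20 to 28 h or later.
- Assessments in between: 180±15 min and 24±4 h (dermatologist, subject, instruments) and 360±15 min (instruments only).

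**Gap under the SAP 5.1 gloss, comparing times**
- Nominal: 24 − 1 = 23 h.
- Using the assessment windows: 20 − 1.25 = 18.75 h to 28 − 0.75 = 27.25 h. The upper value is not a hard maximum, because sunscreen follows the assessments and has no fixed time.
- The 30-minute rule alone would allow application as late as 195 − 30 = 165 min, giving 20 − 165/60 = 17.25 h. That is an outer limit only, since application is meant to follow baseline immediately.

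**How the mismatch depends on the reading**

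| Product that opens the window | Comparison | Counted in Group 1 only |
|---|---|---|
| Test product / sunscreen (SAP 5.1) | times | about 23 h; AEs first seen at 180 min and 24 h |
| Test product / sunscreen (SAP 5.1) | dates | Day 8, including Group 1 onsets before its first application |
| Evening cleanser also counts | times | part of Day 8; AEs first seen at 180 min |
| Evening cleanser also counts | dates | nothing |

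The cleanser rows are arguable because Protocol 5.1 lists the cleanser as a study product and Protocol 7.1.1 includes washout products in the AE definition. Evening cleansing falls after the 360±15-minute measurement. With application by 75 min, the third row's gap is at least 345 − 75 = 270 min, or 4.5 h (3 h at the 165-minute outer limit).

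**Illustration of scale.** The documents give no early AE rate. Let q be the risk of an AE starting in the one-sided period and pl the later risk, equal across arms and independent.
- Group 1 treatment-emergent risk: 1 − (1 − q)(1 − pl). Group 2: pl. Difference: q(1 − pl).
- With 80 randomised and a 1:1 split assumed, the expected spurious Group 1 excess is 40q(1 − pl) subjects.

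| Assumed q | pl = 0 | pl = 20% |
|---|---|---|
| 1% | 0.4 | 0.32 |
| 2% | 0.8 | 0.64 |
| 5% | 2.0 | 1.6 |
| 10% | 4.0 | 3.2 |

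An expected excess of one subject needs q = 1/40 = 2.5% (pl = 0) or 1/(40 × 0.8) = 3.1% (pl = 20%).

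**The case against.** The gloss in SAP 5.1 defines a population, and SAP 9 does not import it. The mismatch runs from about 23 hours to zero depending on the reading, so no particular gap is established. This stands as a limit on the size. It does not rescue the definition: the SAP leaves the choice open, SAP 5.1 is the only place that explains the phrase, and Listing 2.1 carries AE start times, which makes a comparison by time natural. Three of the four readings leave a mismatch.

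Little information is lost. AEs are collected in both arms from the Visit 1 sensitivity test (Protocol 7.2), and Listing 2.1, itself a topline output, shows early events of Safety subjects. The scores that would become AEs are tabulated by arm at 180 minutes and Day 1. This stands, and it keeps the point minor.

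The early rate may be low. Only scores of Severe, or reactions judged worse than expected, become AEs. Subjects scoring Severe on the forearm test are discharged before the peel. Reactions already present at the 60-minute baseline precede any product and, when times are compared, fall outside the window in both arms. This also stands.

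Finally, a supplementary count of all AEs from Day 8 by arm would answer the concern without redefining the term. That is workable, but it leaves the topline table on an undefined window.

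**Conclusion.** The definition needs correcting; severity is minor. Under the only gloss the documents offer, first-day post-peel AEs enter Tables 9.4.1 and 9.4.3 for Group 1 only, over a period of nominally 23 hours, and the bias runs against the test product. This rests on carrying the SAP 5.1 wording into SAP 9. The subject counts are illustrations resting on assumed rates and 1:1 allocation.

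A reader might infer more than the documents support:
- That all four AE tables are distorted alike. Tables 9.4.2 and 9.4.4 hold treatment-related events, and causality is judged against study product (Protocol 7.3). A Group 2 event before any test-phase test product or sunscreen would rarely be judged related, so those two tables are little affected.
- That the trial's conclusion is at risk. Success depends on the dermatologist global assessment in the test-product group alone, and no AE comparison is tested.
- That a 23-hour gap, or a known number of misplaced subjects, is certain. Neither is: the SAP does not settle the reading, and no early AE rate is given.

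**What to change.** In SAP 9, define treatment-emergent AEs in both groups as those starting after completion of the Day 8 post-peel baseline assessments. This is already the baseline for the tolerance and efficacy changes. Use the same anchor for study day in Listing 2.1. Leave the Safety population unchanged, since it is also the basis of the primary Table 9.3.1.

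First confirm that a usable time exists in both arms. Protocol 6.3.21 records the time of test product dispensing, but only Group 1 is dispensed test product. The text available does not say that a baseline or peel-completion time is recorded for both groups. If neither is, count AEs starting on or after the Day 8 date in both groups and say so.

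The cost is one definition and one listing footnote in the SAP, with no protocol change. The downside is that a few events before any product become treatment-emergent, including same-day reactions to the peel alone under the date rule. They do so in both arms alike, so the comparison stays fair.

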6.3.2. Adverse Events

Adverse events will be assessed by the Investigator or designee and recorded on the eCRF, as per the process detailed in Section 7.

As per Section 7.1, the following does not meet the definition of an adverse event: “Any clinically significant abnormal laboratory findings (if applicable) or other abnormal safety assessments which are associated with the underlying disease, unless judged by the investigator to be more severe than expected for the subject’s condition.” Therefore, the Dermatologist (erythema, edema, dryness, and desquamation) and Subject-self assessment (pain, stinging/burning, itching, tightness, redness, and dryness) grades will only be considered adverse events if they are scored as “Severe”, or if the investigator judges them to be more severe than expected in context of the Glycolic Acid treatment procedure.

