7.2. Recording Adverse Events and Serious Adverse Events

Recording of adverse events and serious adverse events:

 1. The investigator or site staff will be responsible for detecting, documenting and reporting events that meet the definition of an AE or SAE. 2. The investigator or site staff will then record all relevant information regarding an AE/SAE in the eCRF. 3. There may be instances when copies of medical records for certain cases are requested by GSK. In this instance, all subject identifiers, with the exception of the subject number, will be blinded on the copies of the medical records prior to submission to GSK. 4. The investigator will attempt to establish a diagnosis of the event based on signs, symptoms, and/or other clinical information. In such cases, the diagnosis will be documented as the AE/SAE and not the individual signs/symptoms. Clinical AEs will be described by diagnosis and not by symptoms when possible (e.g., upper respiratory tract infection, seasonal allergy, etc. instead of runny nose). 5. AEs will be collected from the start of the study material sensitivity test at Visit 1 and until 5 days following last administration of the study product. 6. SAEs will be collected over the same time period as stated above for AEs. However, any SAEs assessed as related to study participation (e.g., investigational product, protocol mandated procedures, invasive tests, or change in existing therapy) or related to a GSK concomitant medication will be recorded from the time a subject consents to participate in the study up to and including any follow-up contact. 7. Medical conditions reported prior to the time period for reporting AEs/SAEs should be recorded as part of the subject's medical history.

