8.1 Primary Analysis

The primary evaluation of tolerance will be based on the Evaluator (Dermatologist) global assessment. The trial will be considered a success if the majority of subjects in the test product group have a favorable (“well tolerated”) Evaluator global assessment score.

The Dermatologist will assess the local tolerance of the post-procedure skin care regimen in context of the expected effects of the procedure for each subject using the scale below and document the score on the eCRF. To make this assessment, the Dermatologist will draw on the total set of clinical and subject self-assessment data for each subject. The Dermatologist must be unaware of whether a subject was randomized to test product to protect the blind.

Rating	Description
0 - Product Regimen was Well Tolerated	No clinically significant worsening of the expected signs/symptoms of the procedure. No new signs/symptoms manifest during product use.
1 - Product Regimen was Not Well Tolerated	Clear, clinically relevant worsening of the severity or frequency of expected signs/symptoms of the procedure and/or any occurrence of new, unexpected signs/symptoms during product use.

Descriptive statistics (N, percentage, 95% confidence intervals) will be used to summarize the proportion of subjects in each product group with a favorable Evaluator global assessment of tolerance. The proportions will also be compared between product groups using Chi-square test, and difference in proportion and 95% confidence interval.

To visually inspect the treatment effect on dermatologist total score, a plot across time with the raw means will be produced. The plot will display a different symbol for each treatment group.

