9.3.4.1	Summary of TEWL – Changes from Baseline – PP Population (if needed)	Table 9.3.3.2.1
9.3.5	Summary of Corneometry – Changes from Baseline – ITT Population	Table 9.3.3.2.1
9.3.5.1	Summary of Corneometry – Changes from Baseline – PP Population (if needed)	Table 9.3.3.2.1
9.3.6	Summary of Subject Global Satisfaction – ITT Population	Appendix 3
9.4.1	Treatment-Emergent Adverse Events – Safety Population	Appendix 3

9.4.2	Treatment-Emergent Treatment-Related Adverse events – Safety Population	9.4.1
9.4.3	Treatment-Emergent Adverse Events by Severity – Safety Population	Appendix 3
9.4.4	Treatment-Emergent Treatment-Related Adverse Events by Severity – Safety Population	9.4.3

Figures No.	Table Title (including population)	Template
9.3.2.1	Subject Self-Assessment Scores – Total Score - Safety Population	Figure 9.3.3.1
9.3.3.1	Dermatologist Assessment Scores – Total Score - Safety Population	Appendix 3

Listing No.	Listing Title (including population)	Template
2.1	Adverse Events – Safety Population	Appendix 3
2.2	Adverse Events – Non-randomised Subjects	2.1
2.3	Serious Adverse Events	2.1
2.4	Randomisation Details	Appendix 3

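### TEAEs are defined by onset alone, so an AE already open at first application that then worsens reaches the AE tables only if the site records the worsening as a new AE, which neither document requires

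*SAP*

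**What the plan says.** SAP section 9 defines the term by start date: "Treatment emergent AEs are defined as events that start on or after the first product application in the test phase". It has no clause for an event that began earlier and became worse.

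The planned AE tabulations are these: "Summaries of treatment-emergent AEs (TEAEs), treatment-related TEAEs, TEAEs by severity and treatment-related TEAEs by severity". SAP Appendix 2 matches them with Tables 9.4.1 to 9.4.4, all titled as treatment-emergent; Table 9.4.3, for example, is "Treatment-Emergent Adverse Events by Severity – Safety Population". No table of all AEs is planned.

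The listings are wider: "Adverse events will be listed for the safety population and separately for the non-randomised subjects". Listing 2.1 therefore holds every AE in the Safety population whatever its start date. It is part of the topline outputs in SAP section 11.

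Recording begins well before the cream. Protocol 7.2 says that "AEs will be collected from the start of the study material sensitivity test at Visit 1". Under Protocol 6.3.2, a dermatologist or subject grade is an AE if it is scored Severe, or "if the investigator judges them to be more severe than expected in context of the Glycolic Acid treatment procedure".

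The primary endpoint (SAP 8.1) treats worsening as a mark of intolerance. One criterion for the unfavourable rating is "Clear, clinically relevant worsening of the severity or frequency of expected signs/symptoms of the procedure".

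**The concern.** This is a tolerance trial in skin that has just been peeled. What the cream might do is make an existing reaction worse, and the primary scale is built around that. The AE tables count new onsets. Where a reaction is already open as an AE when the cream goes on, a rise in its intensity can fall outside every AE table.

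SAP 8.2 names reported AEs as part of the secondary assessment of local tolerance. The AE tables are also the only planned summaries that set out event type, relatedness and severity by arm. A subject could be rated as not tolerating the regimen on the primary endpoint and yet contribute nothing to Tables 9.4.1 to 9.4.4 for the same reaction. Whether that happens depends on how the site completes the AE form, which the plan leaves open.

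**Working it through.** No figure in the plan depends on this rule, so there is nothing to reproduce. The check is to follow an AE from onset to output.

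**1. Can an AE be open at first application in a randomised subject?** Protocol 3.1 orders Visit 3 as eligibility review, randomisation, peel, baseline assessments at 60±15 minutes, then first cream application in Group 1. A baseline grade that meets the AE rule in 6.3.2 has a start date before the cream, in a subject who is already randomised. So the answer is yes.

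The washout week contributes little. A Severe score on the forearm sensitivity test leads to discharge (6.1.11, 6.2.8, 6.3.8). Appendix 4 also has active skin disease and relevant irritated skin at the test site rechecked at Visits 2 and 3, before randomisation.

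**2. What happens if the reaction then worsens?**

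- *Baseline grade mild or moderate and not an AE, later Severe.* It first becomes an AE after application. It is a TEAE and is tabulated.
- *Baseline grade moderate but judged worse than expected, so already an AE, later Severe.* It is tabulated only if the rise is entered as a new AE.
- *Baseline grade Severe, so already an AE.* The sign is at the top of its 0–3 scale (6.3.13, 6.3.14) and cannot rise there. AE intensity is a separate scale based on interference with everyday activities (7.3) and can still rise. Again it is tabulated only if entered as a new AE.

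**3. Do the documents say which kind of entry to make?** Some provisions support a new AE. The general definition in Protocol 7.1.1 covers signs, symptoms or disease that are new or exacerbated. Its list of qualifying events includes safety assessments that worsen from baseline and are judged clinically significant.

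Others point to one continuing record. Protocol 7.2 asks for the diagnosis rather than separate signs, 7.3 asks for an intensity assessment for each AE, and 7.5 follows each AE until it resolves or stabilises. The Listing 2.1 template has start and end dates and a frequency/intensity column, but no date for a change in intensity. Neither document states the rule.

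**4. What does one affected subject weigh?** With 80 randomised and equal allocation assumed, each arm has 80/2 = 40. One subject is 1/40 = 2.5 percentage points in a TEAE row, if she has no other event in that row. The documents give no rate of AEs open at baseline and no rate of worsening, so the number of such subjects cannot be derived.

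**5. When does the TEAE period start in each arm?** This affects how a fix must be worded. SAP 5.1 takes test-phase product to be the cream in Group 1 and sunscreen in Group 2. Protocol section 5 allows no sunscreen on Day 8, so the first Group 2 application is at Visit 4, 24±4 hours after the peel. Assume that application follows directly on the assessments and that cleanser does not count:

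- nominal gap: 24 − 1 = 23 h
- shortest: 20 − 1.25 = 18.75 h
- longest: 28 − 0.75 = 27.25 h

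A worsening clause tied to first product would inherit this difference between the arms.

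**The case against.** The strongest reply is that Protocol 7.1.1 already makes worsening an AE. Its general definition covers exacerbation without limiting it to chronic conditions; the narrower item on chronic or intermittent conditions is only one of several examples. A site that follows the general definition would enter a new AE dated after application, and it would be tabulated. This stands as far as it goes: the protocol permits that entry. It does not require it for an AE already open, and steps 2 and 3 of the check show that either practice fits the text.

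The second reply is that the worsening is visible elsewhere. Unfavourable global ratings capture it, the dermatologist and subject scores are tabulated by category and as change from baseline at each time point, and Listing 2.1 can be read subject by subject with 80 randomised. This also stands, and it limits the consequence. It does not supply relatedness and severity by arm, and an updated listing line would carry a start date before the cream.

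The third reply is that few subjects can be affected: the Visit 3 review largely closes the washout route, and about an hour separates the peel from the baseline assessments. That is fair.

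A reader might infer that any reaction that worsens on the cream is missing from all AE tables, or that such events are lost from the report. The documents support neither. A grade that was not an AE at baseline and later becomes one is tabulated, as is worsening recorded as a new AE, and Listing 2.1 keeps the rest.

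**Conclusion.** The point holds in a limited form. The onset-only definition, combined with AE tables confined to TEAEs, means that worsening of an AE open at first application is tabulated only if the site chooses to open a new record. Otherwise its only place among the AE outputs is Listing 2.1, or also Listing 2.3 if it is serious.

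The affected group is mainly subjects whose post-peel reaction was recorded as an AE at the 60-minute baseline. It is probably small, and the documents give no basis for a percentage. The conclusion assumes that some sites' practice would be to update the open record, which the documents neither prescribe nor rule out. The primary analysis is not altered. What is at risk is agreement between the AE tables and the primary tolerance rating, and the change is worth making because it is cheap.

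**What to change.** In SAP section 9, define treatment-emergent AEs as *events that start, or that started earlier and increase in intensity, on or after completion of the Visit 3 post-procedure baseline assessments*. The same origin then applies in both groups, and peel reactions recorded at baseline that do not worsen stay outside the definition.

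Add a recording rule: an increase in intensity of an open AE is entered with its own date. Count the event in Tables 9.4.1 to 9.4.4 at its worst intensity after the origin.

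The cost is a short SAP revision and an eCRF completion instruction, which should be consistent with the AE recording rules in Protocol 7.2. AE counts may rise slightly in both arms.
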